3. STUDY OVERVIEW

3.1. STUDY OBJECTIVES

The primary objective of this study is to evaluate the long-term safety and tolerability of LIQ861 in patients with PAH.

The secondary objective of this study is to evaluate the comparative bioavailability of treprostинil between two formulations of inhaled therapy.

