3.3. DETERMINATION OF SAMPLE SIZE

At least 130 PAH subjects were to be enrolled to ensure that at least 100 completed 2 months of treatment to evaluate the long-term safety and tolerability of LIQ861. The study enrolled 121 subjects and 113 had the Month 2 visit.

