4. ENDPOINTS

4.1. PRIMARY ENDPOINT

The primary endpoint will be the incidence of Treatment-Emergent Adverse Events (TEAEs) and Serious Adverse Events grouped by Medical Dictionary for Regulatory Affairs (MedDRA) System Organ Class, dose level, time on drug, and relationship to dose-titration.

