6. GENERAL ASPECTS FOR STATISTICAL ANALYSIS

6.1. GENERAL METHODS

Subjects differ by treatment history prior to entry to Study LTI-301 - the two groups will be referred to as the Transition and Add-On Groups. For all summary tables data will be presented for all subjects (Overall) and by group.

Continuous variables will be summarized using the number of non-missing observations (n), mean, standard deviation (SD), standard error (SE), median, minimum and maximum. Categorical variables will be summarized using frequencies and percentages.

Categorical shift tables will include marginal totals.

Unless otherwise specified, the estimated mean and median for a set of values should be printed out to 1 more decimal place than the original values, and SD and SE should be printed out to 2 more decimal places than the original values. The minimum and maximum should report the same number of decimal places as the original values.

Percentages will be displayed with 1 decimal place; except percentages will not be presented when the count is zero and 100% will be presented as an integer. The number of subjects in the analysis population will be the denominator.

Unless stated otherwise, baseline will be taken as the last available non-missing assessment prior to study drug administration (Day 1).

In by-visit summary tables, the baseline will be summarized using all available data, but also for each visit using only the baseline data from subjects with available data at the visit; hence the mean change from baseline will equal the mean visit value – mean baseline value.

Throughout this document ‘change from baseline’ refers to the actual change from baseline (i.e. visit value – baseline value).

All data will be listed separately for each group. Data listings will present study days in addition to dates, where study day is derived as (assessment date – first day of dosing + 1).

Since there is no formal hypothesis testing, no adjustment for multiplicity will be made for inferential statistical comparisons within or between groups.

Programming of analyses, tables and listings will be performed using R Version 3.4.0 or higher (R Foundation for Statistical Computing, Vienna, Austria) or SAS® Version 9.3 or higher (Cary, North Carolina, US).

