7. DEMOGRAPHIC, OTHER BASELINE CHARACTERISTICS AND MEDICATION

7.1. PATIENT DISPOSITION AND WITHDRAWALS

For all subjects screened the following will be presented:

- Number of subjects screened
- Number (%) of subjects who failed screening
- Number (%) of subjects who met the eligibility criteria, but didn't enter the study treatment phase (with reasons)

The above information will only be presented in the 'Overall' column and percentages will use the number of subjects screened (i.e. Screened population) as the denominator.

For the Safety population the following will be presented:

- Number of subjects dosed (Enrolled)
- Number (%) of subjects who withdrew from the study (along with reasons)
- Number (%) of subjects who completed the study
- Number (%) of subjects who chose to enter the extension study (Study LTI-302)

- Number (%) of subjects in each analysis population

Percentages will use the number of subjects dosed (i.e. Safety population) as the denominator.

A Kaplan-Meier plot will present the time to study drug discontinuation. Subjects who transition to Study LTI-302 will be censored on the day of their transition.

For each scheduled visit the following will be presented using the Safety population:

- Number (%) of subjects who had the potential to reach the visit
- Number (%) of subjects who attended the visit (including only clinic visits)
- Number (%) of subjects who withdrew from the study prior to the visit
- Number (%) of subjects who missed the visit

Their potential to reach a visit is based on the duration of time they could have been in the study, from their first dosing date till their date of transitioning to Study LTI-302 or, for those subjects who withdraw from LTI-301, the date when subjects started transitioning to LTI-302 (18th July 2019).

The algorithm will be:

1. Did they have the visit within 7 days of their last dose of study treatment?
 - a. If yes, then **Yes to Potential and Attended Visit**
 - b. If no, go to 2
2. Did they have the potential to have the visit?
 - a. If yes, then go to 3
 - b. If no, then **No to Potential**
3. Did they withdraw prior to the visit?
 - a. If yes, then **Yes to Potential and Withdraw prior to the visit**
 - b. If no, then **Yes to Potential and Missing**

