The number and percentage of subjects with TEAEs will be presented by system organ class (SOC) and PT for both the Safety and mITT populations. Subjects with multiple TEAEs within a SOC or SOC/PT combination will be counted only once for that SOC or SOC/PT combination.

A similar summary will be presented for the Safety population of TEAEs considered as study drug related.

The 'all causality' summary will also be produced using the Safety population for the following:

- the subgroups in Section 6.3
- those TEAEs with an onset up to the Month 2 visit (inclusive) and those with an onset after the Month 2 visit separately.

SOC and PT summaries of TEAEs by maximum severity (mild, moderate or severe) will be presented for all TEAEs and also for those considered as related to study drug.

All summaries will be ordered by descending frequency of total number of subjects within each SOC and then similarly by decreasing frequency of total number of subjects within each PT, in the overall column. In cases of SOCs or PTs with equal frequencies, AEs will be sorted alphabetically.

All TEAEs will be listed by subject and AE onset day. AE duration (stop date/time – start date/time) will be included in the listing; where applicable imputed data will be used for the calculation of AE duration, but the original date information will be presented in the listing.

The following separate listings will also be provided:

- serious AEs
- TEAEs leading to study drug discontinuation (i.e. TEAEs reported as having either an action taken as 'Drug Withdrawn') and/or Study Discontinuation

If there are any deaths a listing will include the date of death and the adverse event(s) associated with death.

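### The single split of TEAEs at the Month 2 visit uses crude percentages over periods of unequal length, so early and late incidence cannot be compared from the planned tables

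*SAP*

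**What the plan says.** SAP 3.1 gives the aim: "The primary objective of this study is to evaluate the long-term safety and tolerability of LIQ861 in patients with PAH". SAP 4.1 makes the primary endpoint the incidence of TEAEs and SAEs grouped by "System Organ Class, dose level, time on drug, and relationship to dose-titration".

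SAP 8.1 sets the statistic: "The number and percentage of subjects with TEAEs will be presented by system organ class (SOC) and PT", with each subject counted once per SOC or SOC/PT combination. Time on drug enters in one way only. The TEAE overview and the all-causality SOC/PT table are each repeated, on the Safety Population, for "those TEAEs with an onset up to the Month 2 visit (inclusive) and those with an onset after the Month 2 visit separately".

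SAP 6.1 gives the general rule for percentages: "The number of subjects in the analysis population will be the denominator". Section 8.1 makes no exception, so the denominator is 121 overall (55 Transition, 66 Add-On; SAP 5.2) in both periods. SAP 3.3 reports: "The study enrolled 121 subjects and 113 had the Month 2 visit".

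Unequal follow-up is recognised elsewhere in the SAP. For the Kaplan-Meier plot of drug discontinuation, Section 7.1 states: "Subjects who transition to Study LTI-302 will be censored on the day of their transition". Sections 6.2.5, 7.1, 7.5 and 9.2 take account of subjects who could not have reached a visit or who withdrew before it. None of this carries over to the TEAE tables.

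**The concern.** Two features of the split affect how its percentages read.

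- **Length of the periods.** The first is about 2 months for most subjects. The second runs until withdrawal or transition to LTI-302, so its length depends on enrolment date and on when the subject left. A crude percentage rises with observation time even when the underlying rate does not change.
- **Risk set.** Most subjects who stopped early have no treatment-emergent time after Month 2, yet they stay in the later denominator. This pulls the later percentage down.

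The two effects act in opposite directions and their net size is unknown from the tables. A reader who sets the two parts side by side could conclude that risk rises, holds or falls with longer use, and any of these could be wrong. The Transition and Add-On columns would carry the same difficulty if their follow-up differs. Data through Month 2 have already been reported (SAP 2), so the later part is what the final report adds on adverse events over longer use.

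**Working it through.** **Inputs from the documents**

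- Safety Population: 55 + 66 = 121 (SAP 5.2), which agrees with SAP 3.3.
- With a Month 2 visit: 113; without: 121 − 113 = 8, or 8/121 = 6.6% (SAP 3.3).
- Month 2: Study Day 56 in SAP 7.5, target Day 60 (window Day 46 to 90) in SAP 6.4. Neither section sets the date of the TEAE cut for a subject who had no Month 2 visit.
- End of the treatment-emergent period: 7 days after the last dose (SAP 8.1).
- Follow-up after Month 2: not given. The visit windows in SAP 6.4 list visits to Month 16 and a general rule beyond.

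The plan states no expected TEAE incidence, so there is no figure of its own to reproduce on this point.

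**Step 1: denominator.** Assume that the 113 stand for those at risk after Month 2. The printed percentage is then the at-risk percentage × 113/121 = 0.934. A true 30% prints as 28.0%; a true 50% prints as 46.7%.

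**Step 2: unequal length, constant hazard.** Let h be an assumed monthly hazard of a first event within the period, and m the months after Month 2, taken as equal for all.

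- First period: 1 − exp(−2h)
- Second period: (113/121) × [1 − exp(−h·m)]

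| h per month | First period | Second, m = 2 | m = 4 | m = 8 | m = 12 |
|---|---|---|---|---|---|
| 0.02 | 3.9% | 3.7% | – | – | 19.9% |
| 0.05 | 9.5% | 8.9% | 16.9% | 30.8% | 42.1% |
| 0.10 | 18.1% | 16.9% | – | – | 65.3% |

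Within each row the risk per month is the same throughout. At h = 0.05 the second figure ranges from slightly below the first to 42.1/9.5 = 4.4 times it.

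**Step 3: a true fall.** Take h = 0.20 up to Month 2 and 0.05 afterwards. The first period reads 1 − exp(−0.4) = 33.0%. The second reads 8.9%, 24.2%, 36.7% or 47.0% for 2, 6, 10 or 14 further months. From 10 months on, a four-fold fall prints as a rise.

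**Step 4: variable follow-up.** The function 1 − exp(−h·m) is concave in m, so spreading follow-up around the same mean lowers the result. With h = 0.05, half the subjects at 2 months and half at 14 (mean 8), the second period reads (8.9 + 47.0)/2, about 28%, against 30.8% when all have 8 months. The second-period figures in Step 2 are therefore upper values for a given mean.

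**Step 5: what a rate would show.** In Step 2 with h = 0.05, the first-event rate is 0.05 × 12 × 100 = 60 per 100 patient-years in both periods. In Step 3 it is 240 and then 60. The rate recovers what the percentages hide.

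**The case against.** The study is descriptive, with no hypothesis test (Protocol 8.4), and the SAP does not say that the two parts will be compared. The Month 2 cut has a plain reason, since data to that point were already reported. The plan also gives total TEAE counts in the overview, treatment duration as a continuous and a banded variable, attendance and withdrawal by visit, and a listing of every TEAE by onset day. A rough overall event rate can be worked out from these. This stands, and it rules out the stronger reading that long-term safety goes unanswered. What is missing is narrower: a rate or at-risk count for each period, at overview or preferred-term level.

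Three further inferences are tempting and not supported.

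- A reader might infer that a subject who stopped before Month 2 can have no later TEAE. The 7-day tail in SAP 8.1 allows it: a last dose on Day 57 and an event on Day 62 would count as after a Day 60 cut.
- A reader might take 113 as the exact number at risk. Some of the 8 may have missed the visit while still on drug, and some of the 113 may have stopped at it or soon after. The factor 0.93 is approximate and could err either way.
- A reader might infer that a constant risk must print as a rise. With only 2 further months it prints as a slight fall (9.5% to 8.9%).

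The large figures in the working rest on assumed hazards and equal follow-up. They show how far the display can mislead, not what it will show.

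**Conclusion.** The point holds in a limited form. The SAP implements time on drug only through two crude percentages on the same 121 subjects, over one period of about 2 months and one that is open-ended and varies by subject. It plans no person-time and no at-risk count for TEAEs, so early and late incidence cannot be compared from the planned tables.

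Unequal length is the main effect: 9.5% against 8.9% to 42.1% at a constant 5% per month, assuming equal follow-up of 2 to 12 further months. Variable follow-up would lower the later figures, and the actual distribution is not in the documents. The denominator effect is secondary, about 6.6% relative, and depends on treating the 113 as those at risk.

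This should be fixed, because it concerns a named component of the primary endpoint and the remedy is cheap. It does not invalidate the safety analysis: no decision rule depends on these percentages, and the counts, exposure and listings remain usable.

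**What to change.** Amend SAP 8.1, as SAP 2 allows before database lock:

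1. Define one Month 2 cut for all TEAE tables, including for subjects without that visit, and reconcile Day 56 (SAP 7.5) with Day 60 (SAP 6.4).
2. For the tables after the cut, use as denominator the subjects whose treatment-emergent period, to 7 days after the last dose, extends beyond the cut. Requiring a dose after the cut would not do, because events in the 7-day tail could then enter the numerator without the subject being in the denominator.
3. For each period and group, add the number of subjects with a first event in the period per 100 patient-years at risk. Person-time ends at the event, the end of the treatment-emergent period or transition to LTI-302, whichever comes first, and events are counted over the same time.
4. Preferably split the time after Month 2 further, for example Months 2–4, 4–8, 8–12 and later. One rate over the whole later period would average out any change within it.

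The cost is SAP wording and extra table columns, from onset and dose dates already collected. Some later percentages will look slightly less favourable, and rates in the latest intervals may rest on few subjects.

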8.2. LABORATORY EVALUATIONS

Laboratory safety parameters are to be assessed at Screening, Baseline, Week 2 and Months 1, 2, 4 and every 12 months thereafter.

Observed and change from baseline clinical laboratory data (including hematology and blood chemistry parameters) will be summarized using descriptive statistics, for Months 2 and 4.

A shift from baseline table for Months 2 and 4 will be presented. Normal, abnormal low, abnormal high and missing records will be summarized, with marginal totals, using frequencies and percentages.

In addition to summarizing by visit the last ‘on-treatment’ measurements will also be summarized. The last ‘on-treatment’ measurement must be after Day 1 and within 1 day of the final dose of LIQ861.

All individual laboratory results will be listed. The listing will include change from baseline values and values outside the laboratory reference range will be flagged.

All pregnancy laboratory results (serum and urine) will be listed.

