	
AUC that is extrapolated beyond the last measurable concentration (AUCext), the terminal phase rate constant (λz), the apparent systemic clearance (CL/F), the apparent volume of distribution in the terminal phase (Vz/F), mean residence time (MRT), and the terminal phase half-life ($t^{1/2}$) will be calculated using non-compartmental analyses.
 
• An assessment of comparative bioavailability of treprostinil will also be made between LIQ861 and Tyvaso based on dose-normalized AUCinf calculations for the two treatments.
STATISTICAL CONSIDERATIONS	
• Individual and mean plots of plasma concentrations versus time after administration of treprostinil will be constructed and displayed for relevant treatment comparisons.• Plasma concentrations will be summarized by treatment using descriptive statistics (sample size, mean, median, coefficient of variation [CV%], standard deviation [SD], minimum, and maximum). Corresponding by-patient data listings will be tabulated.• Derived plasma PK parameters will be summarized by treatment using descriptive statistics (sample size, arithmetic and geometric mean, CV%, SD of the arithmetic mean, median, minimum, and maximum).• The number and percentage of patients who experience at least 1 AE will be presented by severity, relationship to study drug, MedDRA System Organ Class (SOC), preferred term, and dose level of one or both drugs administered. Clinically significant vital signs findings and changes from Baseline values will be tabulated and summarized. Clinical laboratory results will be tabulated.

TABLE OF CONTENTS

PROTOCOL APPROVAL PAGE	2
INVESTIGATOR PROTOCOL AGREEMENT	3
SUMMARY OF AMENDMENT CHANGES.....	4
SYNOPSIS	6
TABLE OF CONTENTS	12
1. INTRODUCTION	17
1.1. Background & Rationale for LIQ861 Development.....	17
1.2. Description of LIQ861	18
1.3. Development Program	19
1.4. Rationale for the Current Study	19
2. STUDY OBJECTIVES	19
3. INVESTIGATIONAL PLAN	19
3.1. Overall Study Design and Plan	19
3.2. Endpoints	21
3.2.1. Primary Endpoint	21
3.2.2. Safety Endpoints	21
3.2.3. Pharmacokinetic Endpoints.....	22
3.2.4. Exploratory Endpoints	22
4. SELECTION OF STUDY POPULATION	22
4.1. Inclusion Criteria.....	22
4.2. Exclusion Criteria.....	23
4.3. Removal of Patients from Therapy/Premature Discontinuation	24
5. TREATMENTS	25
5.1. Treatments Administered	25
5.2. Identity of Investigational Product(s).....	25
5.2.1. LIQ861	25
5.2.2. Labeling.....	26

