6.4. VISIT WINDOWS

Data will be assigned to visits using windowing (see table below). If more than one assessment (including the early termination or unscheduled assessments) falls within the same defined window, the assessment closest to the target day with non-missing data will be considered for analysis; however, with the exception of laboratory and vital sign data, the visit must be within 7 days of the final dose of study treatment. For laboratory and vital sign data the assessment must be no more than 1 day after the final dose of study treatment. If two qualifying assessment dates are at the same distance from the target day, the latest assessment with non-missing data will be taken for analysis.

Visit	Target Day	Analysis Window	Interval
Baseline ^a	1 ^b	Day -30 to Day 1	
Week 2	14	2 -22	21
Month 1	30	23 – 45	23
Month 2	60	46 – 90	45

Visit	Target Day	Analysis Window	Interval
Month 4	120	91 – 150	60
Month 8	240	211 – 270	60
Month 12	360	331 – 390	60
Month 16	480	451 – 510	60
Month m	30m	(30m - 29) – (30m + 30)	60

^a Baseline is the last assessment taken prior to the start of study treatment.

^b Day 1 represents the first day of study treatment.

Please note that telephone visits are not included as only log data will be collected at those visits (e.g. AEs and concomitant medications).

These visit windows will be reviewed and may be updated prior to reporting. Any assessments that fall outside of these windows will be reviewed on a case-by-case basis, and decisions on their handling will be fully documented prior to reporting. Data collected outside these windows will only be listed.

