8.3. VITAL SIGNS

Vital signs are to be assessed at Screening, Baseline, Week 2 and Months 1, 2, 4 and every 12 months thereafter.

Observed and change from baseline data will be summarized using descriptive statistics for Months 2 and 4.

In addition to summarizing by visit the last ‘on-treatment’ measurements will also be summarized. The last ‘on-treatment’ measurement must be after Day 1 and within 1 day of the final dose of LIQ861.

Vital signs data will be listed, with changes from baseline values included.

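### The planned laboratory tables give no count of patients ever out of range on LIQ861, and the synopsis table of clinically significant vital signs has no counterpart in the SAP

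*SAP*

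**What the plan says.** **Collection.** SAP 8.2: "Laboratory safety parameters are to be assessed at Screening, Baseline, Week 2 and Months 1, 2, 4 and every 12 months thereafter". SAP 8.3 gives the same schedule for vital signs. Protocol 6.3 also allows laboratory tests at unscheduled visits.

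**Laboratory tables.** SAP 8.2 plans descriptive statistics for Months 2 and 4, and then: "A shift from baseline table for Months 2 and 4 will be presented". It adds a summary of the last on-treatment measurement, where the "measurement must be after Day 1 and within 1 day of the final dose of LIQ861". It does not say whether that summary includes a shift. All results are listed, with out-of-range values flagged.

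**Selection within a window.** SAP 6.4: "If more than one assessment (including the early termination or unscheduled assessments) falls within the same defined window", then "the assessment closest to the target day with non-missing data will be considered for analysis". Timing is also limited: "For laboratory and vital sign data the assessment must be no more than 1 day after the final dose of study treatment".

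**Vital signs.** SAP 8.3: "Observed and change from baseline data will be summarized using descriptive statistics for Months 2 and 4". A last on-treatment summary and a listing follow. No shift, threshold or clinical-significance table is planned. The protocol synopsis, under Statistical Considerations, says: "Clinically significant vital signs findings and changes from Baseline values will be tabulated and summarized".

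**The concern.** The primary objective is long-term safety and tolerability. A basic safety question for laboratory data is how many patients went out of range at any time on drug, and the planned tables do not answer it. They describe each patient near Day 60, near Day 120 and at the end of treatment.

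A patient with an abnormal unscheduled result on Day 75 and a normal scheduled result on Day 60 appears as normal in the Month 2 shift. Week 2 and Month 1 results fall in the early titration period and have no by-visit table, although the primary endpoint names relationship to dose titration. By contrast, the exploratory measures in SAP 9.1 to 9.3 (6MWD, NYHA class, NT-proBNP) are all summarized at Week 2. After Day 150 there is no by-visit laboratory or vital-signs table at all.

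For vital signs there is also a plain mismatch: the synopsis commits to a table that SAP 8.3 neither plans nor withdraws.

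**Working it through.** **1. The plan's own windows (SAP 6.4).** Length = last day − first day + 1.
- Week 2: 22 − 2 + 1 = 21
- Month 1: 45 − 23 + 1 = 23
- Month 2: 90 − 46 + 1 = 45
- Month 4: 150 − 91 + 1 = 60

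All four match the stated intervals. From Day 2 to Day 150 there are 149 days. The tabulated windows (Months 2 and 4) cover Days 46–150, or 105 days. The remaining 44 days (Days 2–45; 44/149 = 29.5%) feed no by-visit laboratory or vital-signs table. They hold 2 of the 4 scheduled laboratory sets through Month 4.

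**2. Where an out-of-range laboratory value can appear.**

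| Value | By-visit shift | Last on-treatment summary | TEAE tables | Listing |
|---|---|---|---|---|
| Nearest Day 60 or Day 120 in its window | Yes | Only if last | Only if recorded as an AE | Yes |
| Week 2 or Month 1 | No | Only if last | Only if recorded as an AE | Yes |
| Unscheduled, not nearest target | No | Only if last | Only if recorded as an AE | Yes |
| Annual visit after Month 4 | No | Only if last | Only if recorded as an AE | Yes |

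The direction follows from this. The tabulated values are a subset of all on-treatment values, so a count of patients out of range from the first cannot exceed a count from the second.

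**3. Illustration of size.** Assume one abnormality lasting L days, with onset uniform over Days 2–150, samples taken exactly on Days 14, 30, 60 and 120, and no unscheduled samples. A sample on day s catches the abnormality if onset falls on days s − L + 1 to s.

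- L = 14. Onset days caught: 13 for Day 14 (Days 2–14) and 14 each for Days 30, 60 and 120, with no overlap. On a tabulated day (60 or 120): 28/149 = 18.8%. On any scheduled day: (13 + 3 × 14)/149 = 55/149 = 36.9%.
- L = 30. Tabulated: Days 31–60 and 91–120, 60/149 = 40.3%. Any scheduled: Days 2–60 and 91–120, (59 + 30)/149 = 89/149 = 59.7%.
- L = 60. Tabulated: Days 2–120, 119/149 = 79.9%. Any scheduled: the same 119/149 = 79.9%.

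The gap is wide for short abnormalities and zero at 60 days. The documents give no duration, so none of these figures is a forecast.

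**4. Vital signs.** The synopsis promises a table of clinically significant findings, while SAP 8.3 has descriptive statistics and a listing. Protocol 6.5 and 6.6 require the investigator to judge the clinical significance of out-of-range laboratory values and physical examination findings. Protocol 6.7 asks for no such judgment on vital signs. Whether the eCRF holds a flag cannot be seen from the documents.

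**The case against.** A reader might infer that abnormal values vanish from the safety tables altogether. The documents do not support that.

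- **Adverse event route.** Clinically significant laboratory values must be recorded as AEs (Protocol 6.5), and clinically relevant abnormal assessments, vital signs included, as TEAEs or SAEs if they meet the definition (Protocol 7.1, 7.6.5). SAP 8.1 counts patients with TEAEs at any time up to 7 days after the last dose. An unwell patient with an unscheduled sample is a likely case for this route.
- **Unscheduled values are not excluded as such.** SAP 6.4 admits them, and uses one when it is nearest the target. No count of unscheduled samples is given, so the share lost cannot be stated.
- **The last on-treatment summary is not biased towards recovery by rule.** It takes the last value, which can be the abnormal one if a patient stops during the abnormality.
- **Vital signs are not reduced to means.** SAP 6.1 includes the median, minimum and maximum, so the extremes among the tabulated values are visible.
- **The stated endpoint is delivered.** Protocol 3.2.2 asks for change to Month 2/Early Termination; SAP 4.2 adds Month 4. Nothing promises a worst-value laboratory table.
- **Earlier reporting.** SAP 2 says data through Month 2 were reported under an earlier SAP. Week 2 and Month 1 may have been tabulated there.

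All of this stands and narrows the point. It does not close it. The AE route depends on the investigator's judgment, and events are reported as diagnoses where possible (Protocol 7.6.1), so preferred-term counts are not counts of patients out of range. A listing gives no rate. The Month 2 report cannot cover later values.

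**Conclusion.** The point holds as a gap in summary, not as a loss of data. In the final report, out-of-range laboratory values that are neither nearest Day 60 or Day 120, nor last on treatment, nor recorded as AEs appear only in a listing, and no table counts patients ever out of range.

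The firm measures of size are 2 of 4 scheduled laboratory sets and 44 of 149 days through Day 150 without a by-visit table. The patient-level effect is unknown: under the assumptions above, 18.8% against 36.9% for a 14-day abnormality, and 79.9% for both at 60 days. The vital-signs point is a documentary mismatch between synopsis and SAP and needs no assumption.

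The Month 2 and Month 4 tables are legitimate for the endpoint they serve. The change is a cheap improvement that should be made because safety is the primary objective. It does not correct an invalid analysis.

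**What to change.** **SAP 8.2.** Keep the Month 2 and Month 4 tables. Add a shift from baseline to the worst on-treatment value, lowest and highest separately for each parameter. Use all scheduled and unscheduled results after the first LIQ861 dose and up to 1 day after the final dose, annual visits included. State that this table is exempt from the one-value-per-window rule and the listing-only rule in SAP 6.4. In the PK sub-study, the 4-hour sample on Day 1 precedes LIQ861 (Protocol 6.2.3) and should be left out. Also state whether the last on-treatment summary includes a shift.

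**SAP 8.3.** Add the synopsis table of clinically significant vital-sign findings. Use the eCRF flag if one exists, and otherwise vital-sign findings recorded as TEAEs. If the table is no longer wanted, document its removal.

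**Cost.** One laboratory table from data already collected, one vital-signs table or a sentence removing it, and no change to study conduct. Worst-value counts will be at least as high as single-visit counts, and usually higher, because each patient has more chances to be out of range. A footnote should say so, to prevent a direct comparison with the Month 2 and Month 4 tables.
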